6.5.4.1 Hematology

Complete blood count consisting of red blood cell (RBCs), a total white blood cell count with differential (total neutrophil [including bands], lymphocyte, monocyte, eosinophil, and basophil counts), hemoglobin and platelet count.

The above parameters results should be available locally before dosing to verify hematology profile of the patient.

6.5.4.2 Coagulation

Only for patients \geq 18 years old: The coagulation profile includes a prothrombin time (PT) or international normalized ratio (INR), activated partial thromboplastin time (aPTT), and fibrinogen. The assessments must be performed by the central lab along with the standard hematology assessments.

The above parameters results should be available locally before dosing to verify coagulation profile of the patient.

6.5.4.3 Immunoglobulins (IgA, IgE, IgG, IgM)

For total immunoglobulin measurements, assessment of total serum IgG, IgG subclasses, IgM, IgE and IgA and will be performed by the central lab with the standard hematology assessments. If immune parameters are abnormal at end of treatment and are considered clinically significant, patients must be followed monthly until values have returned to baseline or until 6 months after the last dose and at the discretion of the Investigator.

6.5.4.4 Clinical chemistry

If needed to verify postmenopausal status, a FSH test will be performed at screening (Visit 1).

Aldolase, albumin, alkaline phosphatase, total bilirubin (direct and indirect), calcium (total and ionized), cholesterol (total cholesterol, HDL cholesterol, LDL cholesterol), high sensitivity C-reactive protein (hsCRP), creatinine (including calculation of GFR), CK, γ -GT, glucose, IL-6, inorganic phosphorus, lipase, amylase, magnesium, potassium, total protein, AST, ALT, PTHrP, sodium, triglycerides, urea or BUN and uric acid will be assessed.

If the total bilirubin concentration is increased above 1.5 times the upper limit of normal, direct and indirect reacting bilirubin should be differentiated.

The clinical chemistry results (same as above except IL-6, PTHrP and aldolase) should be available locally before dosing to verify clinical chemistry profile of the patient.

For patients 12-17 years old PTHrP, aldolase and fasted plasma glucose are not required.

6.5.4.5 Muscle enzymes

Cardiac troponin-T (cTnT), creatine kinase (CK) and the MB isoenzyme of CK (CK-MB) will be assessed by the central lab along with the standard clinical chemistry assessments.

The cTnT or cTnI parameters results should be available locally before dosing to verify profile of the patient.

For patients 12-17 years old cTnT testing is not required.

A midstream urine sample (approx. 30 mL) will be obtained, in order to avoid contamination with epithelial cells and sediments, and allow proper assessments.

Page 117

A semi-quantitative "dipstick" evaluation for the following parameters will be performed: specific gravity, pH, glucose, protein, bilirubin, ketones, leukocytes and blood.

A "dipstick" evaluation should be available locally before dosing.

If the dipstick result is positive for protein leucocytes or blood, the sample will be sent for microscopic analysis of WBC, RBC and casts.

6.5.5 Pregnancy

Pregnancy tests are required of all female patients regardless of reported reproductive / menopausal status. Serum pregnancy tests will be performed at screening and at End of Study at all other times urine pregnancy tests may be used. The result of this test must be received before the patient is dosed.

6.5.6 Electrocardiogram (ECG)

A standard 12 lead ECG will be performed. Interpretation of the tracing must be made by a qualified physician and documented on the ECG section of the eCRF. Each ECG tracing should be labeled with the following and kept in the source documents at the study site:

- study number •
- patient initials •
- patient number
- date and time

Only clinically significant abnormalities should be reported on this page. Clinically significant abnormalities should also be recorded on the relevant medical history/Current medical conditions eCRF page. Clinically significant findings must be discussed with the sponsor. The clock on the ECG machine should be synchronized with the central clock on a daily basis. The eCRF will contain:

- date and time of ECG •
- heart rate
- PR interval
- QT interval (uncorrected) •
- OTcF •
- **QRS** duration •

The overall interpretation will be collected with a Yes/No statement to confirm if any clinically significant abnormalities are present which need to be specified further.

Original ECG tracings, appropriately dated and signed, will be archived at study site.

Confidential

Corporate Confidential Information

6.5.8 Meal record

Not applicable.

6.6 Pharmacokinetics and Immunogenicity

Blood samples for the analyses of pharmacokinetics (PK) and immunogenicity of MCS110 will be collected during the study from all patients. In addition, synovial fluid samples for the analysis of MCS110 concentration will be collected, if possible, from patients who may undergo surgery.

6.6.1 Analytical methods

Corporate Confidential Information

The detailed method descriptions of the PK and Immunogenicity assays will be included in the corresponding bioanalytical data reports.

6.7 Other assessments

Corporate Confidential Information

6.7.2 Health-related quality of Life (mHAQ and EQ-5D)

During this study the following questionnaires will be utilized mHAQ and EQ-5D for quality of life. Patients must complete the questionnaires before other clinical assessments at any given visit. Investigational staff will not influence, through verbal or other attitudes, the completion of self-administered questionnaires.

Completed questionnaires will be reviewed and examined by the investigator before the clinical examination for responses which may indicate potential AEs or SAEs. The investigator should review not only the responses to the questions in the questionnaires but also for any unsolicited comments written by the patient.

If the occurrence of AEs or SAEs is confirmed, the physician must record the events as per instructions given in Section 7.2 of the protocol. Investigators should not encourage the patients to change the responses reported in the Patient-Reported Outcome (PRO) questionnaires.

7 Safety monitoring

7.1 Adverse events

An adverse event is the appearance or worsening of any undesirable sign, symptom, or medical condition occurring after starting the study drug even if the event is not considered to be related to study drug. Study drug includes the investigational drug under evaluation and the comparator drug or placebo that is given during any phase of the study. Medical conditions/diseases present before starting study drug are only considered adverse events if they worsen after starting study drug. Abnormal laboratory values or test results constitute adverse events only if they induce clinical signs or symptoms, or are considered clinically significant, or require therapy.

The occurrence of adverse events should be sought by non-directive questioning of the patient at each visit during the study. Adverse events also may be detected when they are volunteered by the patient during or between visits or through physical examination, laboratory test, or other assessments. All adverse events must be recorded on the Adverse Events eCRF with the following information:

- the severity grade (mild, moderate, severe)
- its relationship to the study drug(s) (suspected/not suspected)
- its duration (start and end dates or if continuing at final exam)
- whether it constitutes a serious adverse event (SAE)

A SAE is defined as an event which:

- is fatal or life-threatening
- results in persistent or significant disability/incapacity
- constitutes a congenital anomaly/birth defect
- requires inpatient hospitalization or prolongation of existing hospitalization, unless hospitalization is for:
 - routine treatment or monitoring of the studied indication, not associated with any deterioration in condition
 - elective or pre-planned treatment for a pre-existing condition that is unrelated to the indication under study and has not worsened since the start of study drug
 - treatment on an emergency outpatient basis for an event not fulfilling any of the definitions of a SAE given above and not resulting in hospital admission
 - social reasons and respite care in the absence of any deterioration in the patient's general condition
- is medically significant, i.e., defined as an event that jeopardizes the patient or may require medical or surgical intervention to prevent one of the outcomes listed above

Any required in patient hospitalization after day 33 surgery to complete PVNS tumor resection will not be considered as a serious adverse event.

Unlike routine safety assessments, SAEs are monitored continuously and have special reporting requirements; see Section 7.2.

All adverse events should be treated appropriately. Treatment may include one or more of the following: no action taken (i.e., further observation only); study drug dosage adjusted/temporarily interrupted; study drug permanently discontinued due to this adverse event; concomitant medication given; non-drug therapy given; patient hospitalized/patient's hospitalization prolonged. The action taken to treat the adverse event should be recorded on the Adverse Event eCRF.

Confidential

Once an adverse event is detected, it should be followed until its resolution or until it is judged to be permanent, and assessment should be made at each visit (or more frequently, if necessary) of any changes in severity, the suspected relationship to the study drug, the interventions required to treat it, and the outcome.

Information about common side effects already known about the investigational drug can be found in the Investigator Brochure (IB) or will be communicated between IB updates in the form of Investigator Notifications. This information will be included in the patient informed consent and should be discussed with the patient during the study as needed.

7.2 Serious adverse event (SAE) reporting

Any required in patient hospitalization after day 33 surgery to complete PVNS tumor resection will not be reported as a serious adverse event (only for Part A).

Any required patient hospitalization due to surgery to complete PVNS tumor resection will not be reported as a serious adverse event (for Part B and C).

To ensure patient safety, every SAE, regardless of suspected causality, occurring after the patient has provided informed consent and until 30 days after the patient has stopped study participation (defined as time of last dose of study drug taken or last visit whichever is later) must be reported to Novartis within 24 hours of learning of its occurrence.

Any SAEs experienced after this 30 day period should only be reported to Novartis if the investigator suspects a causal relationship to the study drug.

Recurrent episodes, complications, or progression of the initial SAE must be reported as followup to the original episode, regardless of when the event occurs. This report must be submitted within 24 hours of the investigator receiving the follow-up information. An SAE that is considered completely unrelated to a previously reported one should be reported separately as a new event.

Information about all SAEs is collected and recorded on the Serious Adverse Event Report Form. The investigator must assess the relationship of any SAE to study drug, complete the SAE Report Form in English, and send the completed, signed form by fax within 24 hours to the local Novartis Chief Medical Office & Patient Safety Department. The telephone and telecopy number of the contact persons in the local department of Clinical Safety and Epidemiology, specific to the site, are listed in the investigator folder provided to each site. The original copy of the SAE Report Form and the fax confirmation sheet must be kept with the case report form documentation at the study site.

Follow-up information is sent to the same person to whom the original SAE Report Form was sent, using a new SAE Report Form stating that this is a follow-up to the previously reported SAE and giving the date of the original report. The follow-up information should describe whether the event has resolved or continues, if and how it was treated, whether the blind was broken or not, and whether the patient continued or withdrew from study participation.

If the SAE is not previously documented in the Investigator's Brochure or Package Insert (new occurrence) and is thought to be related to the Novartis study drug, a Chief Medical Office & Patient Safety Department associate may urgently require further information from the investigator for Health Authority reporting. Novartis may need to issue an Investigator Notification (IN) to inform all investigators involved in any study with the same drug that this SAE has been reported. Suspected Unexpected Serious Adverse Reactions (SUSARs) will be collected and reported to the competent authorities and relevant ethics committees in accordance with Directive 2001/20/EC or as per national regulatory requirements in participating countries.

7.3 Pregnancies

To ensure patient safety, each pregnancy occurring after signing the informed consent must be reported to Novartis within 24 hours of learning of its occurrence. When pregnancy occurs in a patient in the study, the **study drug must be discontinued**. The occurrence of pregnancy will trigger unblinding of a given patient (see Section 14.1) for safety purposes. The pregnancy should be followed up to determine outcome, including spontaneous or voluntary termination, details of the birth, and the presence or absence of any birth defects, congenital abnormalities, or maternal and/or newborn complications. The collection of this information could last for up to 3 months following the birth of the child. Similar information will be collected if the partner of a male participant become pregnant while her partner is participating to the study.

Pregnancy should be recorded on a Clinical Trial Pregnancy Form and reported by the investigator to the local Novartis Chief Medical Office & Patient Safety Department. Pregnancy follow-up should be recorded on the same form and should include an assessment of the possible relationship to the Novartis study drug of any pregnancy outcome. Any SAE experienced during pregnancy must be reported on the SAE Report Form.

7.4 Data Monitoring Committee

Not applicable.

8 Data review and database management

8.1 Site monitoring

Before study initiation, at a site initiation visit or at an investigator's meeting, a Novartis representative will review the protocol and eCRF with the investigators and their staff. During the study, the field monitor will visit the site regularly to check the completeness of patient records, the accuracy of entries on the eCRF, the adherence to the protocol and to Good Clinical Practice, the progress of enrollment, and to ensure that study drug is being stored, dispensed, and accounted for according to specifications. Key study personnel must be available to assist the field monitor during these visits.

The investigator must maintain source documents for each patient in the study, consisting of case and visit notes (hospital or clinic medical records) containing demographic and medical

information, laboratory data, electrocardiograms, and the results of any other tests or assessments. All information on eCRFs must be traceable to these source documents in the patient's file. The investigator must also keep the original informed consent form signed by the patient (a signed copy is given to the patient).

Confidential

The investigator must give the monitor access to all relevant source documents to confirm their consistency with the eCRF entries. Novartis monitoring standards require full verification for the presence of informed consent, adherence to the inclusion/exclusion criteria, documentation of SAEs, and the recording of data that will be used for all primary and safety variables. Additional checks of the consistency of the source data with the eCRF are performed according to the study-specific monitoring plan. No information in source documents about the identity of the patients will be disclosed.

8.2 Data collection

Designated investigator staff will enter the data required by the protocol into the Electronic Case Report Forms using fully validated software that conforms to 21 CFR Part 11 requirements. Designated investigator site staff will not be given access to the eCRF system until they have been trained. Automatic validation programs check for data discrepancies and, by generating appropriate error messages, allow the data to be confirmed or corrected before transfer of the data to the CRO working on behalf of Novartis. The Investigator must certify that the data entered into the Electronic Case Report Forms are complete and accurate. After database lock, the investigator will receive a CD-ROM of the patient data for archiving at the investigational site.

8.3 Database management and quality control

CRO staff on the behalf of Novartis will review the data entered into the eCRFs by investigational staff for completeness and accuracy and instruct the site personnel to make any required corrections or additions. No obvious corrections are allowed for this study. Queries are sent to the investigational site using an electronic data query. Designated investigator site staff is required to respond to the query and confirm or correct the data. If the electronic query system is not used, a paper Data Query Form will be faxed to the site. Site personnel will complete and sign the faxed copy and fax it back to Novartis staff who will make the correction to the database. The signed copy of the Data Query Form is kept at the investigator site.

- Concomitant medications entered into the database will be coded using the WHO Drug Reference List, which employs the Anatomical Therapeutic Chemical classification system.
- Medical history/current medical conditions and adverse events will be coded using the Medical dictionary for regulatory activities (MedDRA) terminology.
- Laboratory samples will be processed centrally and the results will be sent electronically to Novartis (or a designated CRO).
- MRI data will be processed centrally and the results will be sent electronically to Novartis (or a designated CRO).

Corporate Confidential Information

At the conclusion of a non-IVRS study, the occurrence of any emergency code breaks will be determined after return of all code break reports and unused drug supplies to Novartis. The occurrence of any protocol deviations will be determined. After these actions have been completed and the database has been declared to be complete and accurate, it will be locked and the treatment codes will be unblinded and made available for data analysis. Any changes to the database after that time can only be made by joint written agreement between the Global Head of Clinical Information Sciences and the Clinical Franchise Head.

Corporate Confidential Information

9 Data analysis

9.1 Analysis sets

All patients as randomized that received at least one dose of study drug will be included in the data analysis. Patients will be analyzed according to the treatment actually received - "all patients population".

For patients for which the actual treatment received does not match the randomized treatment the treatment actually received will be used for the analysis.

All patients that received study drug and with no protocol deviations with relevant impact on safety will be included in the safety analysis set.

The PK analysis set will include all patients with at least one available valid (i.e., not flagged for exclusion) PK concentration measurement, who received any study drug and experienced no protocol deviations with relevant impact on PK data.

The PD analysis set will include all patients with any available PD data, who received any study drug and experienced no protocol deviations with relevant impact on PD data.

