Eligibility criteria and safety assessments will be similar as in Part B. Patients will also be followed up to 2 years every 4 months and they will be offered another treatment course with 10 mg/kg of MCS110 in case of relapse, where relapse is diagnosed at least 6 months after the last MCS110 dose received during the first treatment course.

Efficacy assessments will include tumor volume reduction, Corporate Confidential Information joint specific questionnaires, VAS and time to relapse.

[figure not shown]

Figure 2-1: Study design Part C – adults and adolescents

Conditions of lower dose arm recruitment extension

If a lower dose is identified with at least the same efficacy as 10 mg/kg, defined as tumor volume reduction evaluated by MRI of at least 45%, additional patients may be enrolled in this lower dose group to extend the arm up to approximately 10 patients. Only one dose level, either 3 or 5 mg/kg may be extended and the additional patients will be allocated to the selected dose level in an open label fashion with the same assessment schedule applied, Corporate Confidential Information

The planned enrollment number in Part C is approximately 15 patients. If a lower dose is identified to be, at least, as efficacious as 10 mg/kg, additional patients may be enrolled in open label to extend the efficacious 3 mg/kg or 5 mg/kg arm to approximately 10 patients.

3 First interpretable results (FIR)

First interpretable results (FIR) will be provided for this trial for each interim analysis and final analysis.

Corporate Confidential Information

Corporate Confidential Information

5 Statistical methods: Analysis sets

Analysis sets will be defined the same for parts A,B and C.

For subjects for which the actual treatment received does not match the randomized treatment the treatment actually received will be used for the analysis.

All patients that received the study drug dose and with no protocol deviations with relevant impact on safety will be included in the safety analysis set.

All patients with at least one available valid (i.e. not flagged for exclusion) PK concentration measurement, who received the study drug and experienced no protocol deviations with relevant impact on PK data will be included in the PK analysis set.

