All patients with any evaluable PD data who received any study drug (or at least 2 consecutive MCS110 doses for Part B) and experienced no protocol deviations with relevant impact on PD data will be included in the PD data analysis set.

The analysis sets and protocol deviation codes are related as follows:

Table 5-1 Protocol deviation severity codes and analysis sets

Protocol deviation severity code		Safety analysis set	PK analysis set	PD analysis set
Code	Text			
5	Exclude subject from all safety analysis	-	-	-
20	Exclude subject from PK analysis set	+	-	+
22	Exclude subject from PD analysis set	+	+	-
23	Exclude subject from PK and PD analysis set	+	-	-
49	Report relevant protocol deviation – include subject in all analysis sets	+	+	+

+ = include in analysis set, - = exclude from analysis set, NA = not applicable

6 Statistical methods for Pharmacokinetic (PK) parameters

PK analysis set will be used for the PK related summary tables described in this section.

PK data will be listed and summarized by Part A and Part B separately.

Noncompartmental pharmacokinetic analysis will be performed on MCS110 concentration-time profiles and the following PK parameters characterizing the disposition of MCS110 will be generated using WinNonlin Phoenix (Version 6.2, Pharsight, Mountain View, CA):

Part A: AUC_{last}, AUC_{inf}, T_{max}, C_{max}, CL, V_{ss}, and MRT.

Part B: AUC_τ (τ=dosing interval in Part B), R_{acc} (accumulation ratio), T_{max}, C_{max}, T_{1/2}.

Part C: AUC_τ (τ=dosing interval in Part C), R_{acc} (accumulation ratio), T_{max}, C_{max}, T_{1/2}.

Additional PK parameters may be determined and compartmental PK modeling may be performed where appropriate.

Biofluid concentrations will be expressed in mass per volume units. All concentrations below the limit of quantification or missing data will be labeled as such in the concentration data listings. Concentrations below the limit of quantification will be treated as zero in summary statistics and will be omitted for the calculation of pharmacokinetic parameters.

Descriptive statistics of pharmacokinetic parameters will include mean, SD, and CV, min and max. When a geometric mean will be presented it will be stated as such, missing values will be set to zero and excluded for the purposes of calculating the geometric mean. Since T_{max} is generally evaluated by a nonparametric method, median values and ranges will be given for this parameter.

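### The safety set drops dosed patients whose protocol deviation bears on safety; secondarily, the SAP's two-dose condition for the Part B PD set does not match the Protocol

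*Protocol*

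**What the plan says.** **Safety set.** Protocol 9.1 defines it as follows: "All patients that received study drug and with no protocol deviations with relevant impact on safety will be included in the safety analysis set". SAP section 5 keeps the same condition: only dosed patients "with no protocol deviations with relevant impact on safety will be included in the safety analysis set". In SAP Table 5-1, code 5 reads "Exclude subject from all safety analysis" and carries a minus sign for the safety, PK and PD sets. It is the only code that takes a patient out of the safety set. Code 49 is the alternative already in the table: report the deviation, but "include subject in all analysis sets".

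**All dosed patients.** Protocol 9.1 opens with a wider population: "All patients as randomized that received at least one dose of study drug will be included in the data analysis". These patients are analysed by the treatment they actually received. SAP section 5 and Table 5-1 contain no such population.

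**PD set.** The Protocol version has no minimum number of doses: "The PD analysis set will include all patients with any available PD data, who received any study drug". The SAP version covers patients "who received any study drug (or at least 2 consecutive MCS110 doses for Part B"). SAP section 5 begins, however, with "Analysis sets will be defined the same for parts A,B and C".

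**The concern.** Safety and tolerability is a primary objective of every part (Protocol 2.1, 2.4 and 2.7). A safety set exists to describe what happened to people who were exposed. Under this rule, the only dosed patients who can be left out are those whose deviation was judged to matter for safety. Neither document defines what makes the impact relevant, so the decision is a judgement, and it may be made when the patient's adverse events are already known. Leaving such patients out can move adverse event rates in either direction.

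The two documents agree on this rule, so the difficulty is the rule itself and not a conflict between them. It matters most for Part C, whose stated purpose includes an improved adverse event profile at lower doses (Protocol 1.4), with a 10 mg/kg arm planned at about 3 patients (Protocol 5.2.3).

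The PD point is a different kind of problem. It is a mismatch between Protocol and SAP, and between the SAP and its own opening statement. If the SAP clause were applied to the pooled week-4 tumour volume analysis, an outcome already measured would be kept or dropped according to later dosing.

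**Working it through.** The plan gives no figure that depends on these definitions, so there is none to reproduce. The check compares the texts and then illustrates the effect of one exclusion.

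**1. Who can be removed from the safety set**

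| Source | Must have been dosed | Other condition |
|---|---|---|
| Protocol 9.1, all dosed patients | yes, at least one dose | none |
| Protocol 9.1, safety set | yes | no safety-relevant deviation |
| SAP section 5, safety set | yes | no safety-relevant deviation |
| SAP Table 5-1, code 5 | not stated | removed from safety, PK and PD sets |
| SAP Table 5-1, code 49 | not stated | kept in all sets, deviation reported |

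The difference between the first row and the next two is exactly the group of dosed patients with a safety-relevant deviation. Code 5 also goes beyond the PK and PD definitions, which exclude only for deviations affecting PK or PD data.

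**2. Which population the safety tables use.** Protocol 9.7 and SAP section 8, as far as they can be read, name no analysis set for the adverse event tables. Nothing readable directs those tables to the all-dosed population.

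**3. Size of one exclusion (hypothetical).** Counts come from Protocol 3.5.1. With x events in n patients, dropping one patient with the event gives (x − 1)/(n − 1), and dropping one without it gives x/(n − 1).

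| Event | As counted | One with event dropped | One without event dropped |
|---|---|---|---|
| Part B rash | 4/11 = 36.4% | 3/10 = 30.0% | 4/10 = 40.0% |
| Part B periorbital swelling | 6/11 = 54.5% | 5/10 = 50.0% | 6/10 = 60.0% |
| Part C rash | 6/18 = 33.3% | 5/17 = 29.4% | 6/17 = 35.3% |
| Part C periorbital swelling | 15/18 = 83.3% | 14/17 = 82.4% | 15/17 = 88.2% |

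One patient is 1/11 = 9.1% of Part B, 1/18 = 5.6% of Part C, and 1/3 = 33.3% of the planned Part C 10 mg/kg arm.

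**4. PD set and the week-4 analysis.** Part B dosing is on day 1 and then at weeks 4, 8, 12, 16 and 20, each dose after that visit's MRI (Protocol 5.5.4). A patient who starts on MCS110 reaches a second consecutive dose at week 4, after the week-4 scan. A patient who starts on placebo has the first MCS110 dose at week 4 and the second at week 8, both after that scan. So under the SAP clause, every Part B patient's place in a week-4 analysis would depend on dosing after the outcome was measured. SAP 7.1.2 puts 3 of the 5 placebo patients in Part B.

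**5. Whether the PD clause is likely to remove anyone.** Protocol section 1 reports 11 exposed Part B patients and describes them as having received multiple doses. An evaluable Part B patient already needs two MCS110 doses and a follow-up MRI (Protocol 3.2.1, SAP 2.3). Non-safety withdrawals before that point are replaced (Protocol 5.5.9). The number removed is therefore probably small or zero.

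**The case against.** The strongest reply is that the remedy is already in the Protocol. Section 9.1 names a population of everyone dosed, SAP section 8 says all safety data are to be listed and summarised by part unless otherwise stated, and adverse event information is displayed by patient. This is real mitigation for the listings. It does not settle the denominators of the incidence tables, because SAP section 5 omits that population, Table 5-1 provides an exclusion code, and no readable sentence assigns the tables to the wider set.

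A second reply is that, by analogy with the PK and PD definitions, the phrase may refer to impact on safety data and so cover few cases. That narrower reading is possible, but it would still remove exposed patients.

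Third, nothing shows that anyone has been excluded. Protocol 3.5.1 uses the full 11 and 18 exposed patients for rash and swelling. These are narrative counts and not final tables, but they give no sign of an exclusion. This stands.

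Fourth, parts of the SAP are blacked out or missing (section 4, section 9), and the heading of 7.1 seems to have run together with another sentence. The absence of a named set in 7.1 therefore cannot be treated as established. This also stands. That the PD set governs 7.1 is inferred from its place under section 7.

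Two stronger readings are tempting. A reader might infer that patients stopped because of a risky deviation (Protocol 5.5.9) would vanish from the SAP section 8 count of adverse events leading to discontinuation. The documents do not support that: stopping for a deviation is not the same as stopping for an adverse event. A reader might also infer a measurable loss of precision at week 4 from the PD clause. No patient is shown to be lost, and a calculation with a fixed residual SD would not represent the planned model, which gives sigma a prior.

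**Conclusion.** The safety-set point holds. Followed as written, both documents remove exposed patients from the safety set because of a safety-relevant deviation, in a trial where safety is a primary objective of every part. The effect is potential and not shown. With one assumed exclusion, the Part B rates shift by about 4 to 6 percentage points and the pooled Part C rates by about 1 to 5. The conclusion rests on code 5 being applied to dosed patients and on the incidence tables using the safety set. The readable text permits both but confirms neither. The point should be corrected; it does not show that any reported rate is wrong.

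The PD-set mismatch is real as a matter of wording and needs reconciling. Its effect on the week-4 analysis is inferred and probably nil.

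**What to change.** - In SAP section 5, define the safety set as all patients who received any study drug, analysed by treatment received. Make the same change to Protocol 9.1 at the next amendment.
- Do not apply code 5 to dosed patients. Report their safety-relevant deviations under code 49.
- State in SAP section 8 that the safety tables use this set.
- Use the Protocol's PD wording, with no minimum number of doses, for the pooled week-4 analysis, and name the set in SAP 7.1 if the unredacted text does not already do so. If a two-dose condition is wanted, confine it to a sensitivity subset of the multiple-dose summaries.

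Cost: a new SAP version before database lock, under the change procedure in SAP 1.2. The Protocol wording needs a written amendment with the approvals listed in Protocol 11.1, so it can wait for the next one. No extra data collection is needed.
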